9.2.5.4 Vaccinated Case-Coverage Design

For the vaccinated case-coverage analysis, exposure and comparison windows will be defined using the same guidance and considerations as the CCO design, and cases that were vaccinated in either window will be informative to analysis. For each case, the observed odds of vaccination within the exposure window will be estimated and compared with an expected odds of vaccination inside the exposure window, which will be estimated in an external reference population. Data to estimate the expected odds of vaccination may come from population-based registers or surveys, or other secondary data sources that reflect temporal patterns in vaccination among the target population in the catchment areas for cases.

To calculate the expected odds of vaccination in the exposure window for each case, strata comprising all persons in the reference population who are similar to the case with respect to confounder status (e.g., age, sex, and risk factors) on the day of outcome onset will be created. Then the odds of vaccination in the same calendar period equating to the case's exposure window will be computed in the reference population. Reference population individuals in the stratum had to have received the same vaccine during the same calendar periods equating to the exposure or comparison windows before the onset of the case onset date and had to belong to the same groups as the case with regard to predefined confounding factors (e.g., age, sex, high-risk conditions). These predefined confounding factors will be selected on the basis that temporal patterns in vaccination are likely to be different across different levels of the confounder. Of note, this design requires information on vaccination in the reference population by risk factors and calendar date of vaccination. It is anticipated that these data will not be available for the catchment areas of most hospital sites.

Further Considerations for all Designs

For all designs, the risk window will depend on the severe adverse event under study and will be based on biological plausibility, expert input, clinical trials of COVID-19 vaccines, active and passive postmarketing surveillance of COVID-19 vaccines (including spontaneous reporting databases administered by pharmaceutical companies), and safety data from other vaccines (as applicable). Additionally, if the risk interval for an outcome is not well established (e.g., an emerging, unanticipated safety signal), then sensitivity analysis incorporating different definitions of the risk interval should be conducted.

9.2.5.5 Covariate Assessment

In this section, covariates of interest, operational definitions, and purpose for assessment will be described.

Descriptive Covariates

For descriptive purposes, sex, age, country, race/ethnicity (if available), and calendar month of vaccination will be output in the study population.

Confounders

Self-controlled Risk Interval and Case-Crossover Designs

While the SCRI and the CCO implicitly adjust for measured and unmeasured confounders that do not vary over time (e.g., chronic conditions and gender), covariates that vary over time may act as confounders if they affect the risk of the adverse event [4] or affect the timing of seeking care for the adverse event (e.g., provision of health care utilisation due to lockdown periods). Below are some possible time-varying confounders of relevance, though this list will need to be adapted based on the specific study population and outcomes of interest. It is anticipated that not all hospitals will have the ability to capture time-varying variables after hospital discharge.

Age may act as a time-varying confounder in children, depending on the outcome of interest. Age may be adjusted for in the SCRI by dividing person-time during follow-up into prespecified age groups (e.g., weeks or months).

Calendar time as a proxy for circulating wild-type SARS-CoV-2 and other respiratory infections and for health care utilisation (e.g., periods of lockdown) may also act as a time-varying confounder. Separate categorical variables for calendar time can be created by dividing up person-time into the relevant categories of calendar time; the categories should be selected based on the timing of changes in health care utilisation and rates of circulating infection (at the population level), rather than equally spaced categories such as calendar months. It is recommended that hospital site's internal administrative data be used to identify the specific timing of changes in health care utilisation in the population.

Both infections and receipt of other non-COVID-19 vaccines may act as confounders if they increase the risk of the adverse event of interest. Infections relevant to the adverse event of interest (e.g., SARS-CoV-2, influenza-like illness, upper respiratory infection, gastrointestinal infection) will be captured using diagnosis codes in hospital data and primary care data, if feasible. It is anticipated that not all hospitals will be able to collect information regarding individual-level infections for adjustment in the SCRI design because they will not be able to capture information after discharge, and any data obtained directly from primary care providers may require informed consent from patients. Vaccines relevant to the adverse event of interest will be captured in pharmacy dispensing records, general practice records, immunisation registers, medical records, vaccination cards, or other secondary data sources.

Both the SCRI and CCO can adjust for infections and receipt of other non-COVID-19 vaccines. In the SCRI, this is done by categorising the entirety of follow-up time into “exposed” and “unexposed” person-time with respect to infection or vaccination; each infection and non-COVID-19 vaccine will have its own risk window based on the temporal effect of the infection/vaccine on the outcome of interest. In the CCO, infection and vaccine status (yes vs. no) will be assessed separately during the risk and control windows for COVID-19 vaccination.

Vaccinated Case-Coverage Design

The vaccinated case-coverage design is not self-controlled and may be biased if time trends in exposure for calculating the expected odds of vaccination in the exposure window is not the same in cases and in the reference population. Adjustments for any such confounders will be made by matching cases to the reference population on the status of the confounder (e.g., age and sex), as of the case’s index date. To do this, the risk stratum for calculating the expected odds of vaccination in the exposure window for each case will need to be defined accordingly.

[Investigator should add confounders relevant to specific adverse events in this section and provide operational definitions].

Effect Modifiers

In this section, any factors (e.g., age at vaccination, sex, race, chronic conditions, infections, concomitant vaccinations and medications, and dose number) that are hypothesised to modify the effect of COVID-19 vaccination on the adverse event of interest will be listed. Chronic conditions will be identified using diagnosis and procedure codes in inpatient data, outpatient specialist visits, medical records, and primary care data, as available. COVID-19 vaccination is given in multiple doses, dose number will be assessed as a potential effect modifier.

Additionally, health care workers and pregnant women may potentially be specific populations of interest and may be analysed as subgroups. Information on occupational

status may be obtained from administrative or medical records; availability of this information may be incomplete and may not be available in all study sites.

[Investigator should specify the effect modifiers and their operational definitions in this section].

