 - For persons who receive only one dose, define the risk and control intervals as 1 to 42 and 43 to 127 days after vaccination, respectively.
 - In the above scenarios, the control window could be placed even further in time from vaccination to incorporate a washout period between the risk and control intervals, as needed.
- If there is a short interval between doses of the vaccine but the risk interval is short, a dose-level analysis (treating each dose as a separate observation) could be conducted, but care must also be taken to ensure that the control interval does not overlap with the next dose. For example, suppose the vaccine is administered in two doses approximately 28 days apart, and the outcome of interest has a risk interval of 0 to 7 days. The control interval would need to end before 27 days after vaccination (e.g., 8-15 days) to ensure that there is no overlap of the control interval of the first dose with the risk interval of the second dose.

If the outcome affects the likelihood of a subsequent vaccination after the first dose, the impact of this potential bias could be explored in a sensitivity analysis using Farrington’s pseudolikelihood method for perturbed, censored, or curtailed observation periods for postevent exposures [7].

CCO Design

If the CCO design is used, an exposure window preceding the event will be selected to reflect the period during which exposure to COVID-19 vaccination is hypothesised to trigger the adverse event of interest. A single comparison window preceding the risk window will be selected to reflect the baseline prevalence of exposure; the comparison window should be selected independently of exposure status. Multiple comparison windows per case may also be considered but are not recommended because they may increase the potential for bias due to time-varying confounding and temporal trends in

exposure. By convention, the exposure window will index on the date of the adverse event, which will be time = 0. A washout period between the exposure and comparison windows can be implemented to avoid any carryover effects of the vaccine between the two windows.

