If multiple doses are given during the study, the comparison window should be selected such that the underlying propensity to be vaccinated is not correlated between the exposure and comparison window. This guidance is given because individuals who are vaccinated in both windows do not contribute to the analysis and excluding a large number of individuals due to this reason reduces statistical power and precision of risk estimates. As an example, suppose the vaccine dosing schedule calls for two doses approximately 28 days apart, and the risk window is 1 to 21 days prior to the event. If one were to select a control window of 22 to 42 days, we anticipate that many persons would be vaccinated in both windows and become uninformative to the study. To avoid this, the comparison window could be defined as 50 to 70 days before the event; the comparison window could be placed even further before the event to incorporate a washout period between the exposure and comparison window, as needed.

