9.6.2 Measures of Association

If the SCRI is used, conditional Poisson regression (conditioned on the individual) will be used to estimate incidence rate ratios and 95% confidence intervals for each outcome, with logarithm of time in each interval as the offset. If the CCO is used, conditional logistic regression (conditioned on the individual) will be used to estimate odds ratios and 95% confidence intervals for each outcome.

For the SCRI and CCO, time-varying confounders will be adjusted for in regression models. If applicable, in the SCRI, age and calendar time may be categorised into several categories, or treated as polynomial functions, with or without the use of splines in regression models. Both unadjusted and adjusted incidence rate ratios, by site and pooled across all sites, will be reported.

If the vaccinated case-coverage design is used, a logistic regression model will be fit for each AESI under study using separate summarised data sets. The data set for each AESI under study will have one record per risk set (i.e., case), with the outcome indicating whether vaccination occurred in the case's exposure or comparison window. The logarithm of the expected odds (i.e., logit) of vaccination inside the exposure window will be entered into the model as an offset term. For each case, this expected probability of vaccination inside the exposure window will be obtained from the reference population, as described in Annex 3. The model will include only an intercept with no covariate, with the following general form.

$$\text{Logit}(p_1) = \text{logit}(p_0) + \beta_0,$$

where p_1 is the observed probability of vaccination inside the exposure window among cases, p_0 is the expected probability of vaccination inside the exposure window among cases (based on vaccination data in the reference population), β_0 is the intercept; by exponentiating this coefficient, one obtains an odds ratio describing the association between vaccination and the outcome of interest occurring inside the risk interval.

Of note, the logistic regression model drops all cases for whom the expected probability of vaccination inside the exposure window is 0 or 1 (i.e., either everyone or no one is vaccinated inside the risk interval amongst the reference population), as these cases are noninformative.

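### The case-crossover adjustment measures infections and other vaccines over the COVID-19 vaccine's windows, not their own, so it is incomplete when they act longer or later and are linked to vaccination timing

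*Protocol*

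**What the plan says.** Section 9.2.5.5 names the covariates as confounders: "Both infections and receipt of other non-COVID-19 vaccines may act as confounders if they increase the risk of the adverse event of interest". It then gives one measurement rule per design.

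- SCRI: "each infection and non-COVID-19 vaccine will have its own risk window based on the temporal effect of the infection/vaccine on the outcome of interest".
- CCO: "In the CCO, infection and vaccine status (yes vs. no) will be assessed separately during the risk and control windows for COVID-19 vaccination".

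Section 9.2.5.3 sets the CCO window from the COVID-19 vaccine alone: "an exposure window preceding the event will be selected to reflect the period during which exposure to COVID-19 vaccination is hypothesised to trigger". Its worked example for a two-dose schedule has a risk window where "the risk window is 1 to 21 days prior to the event", and says "the comparison window could be defined as 50 to 70 days before the event".

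Section 9.6.2 carries the covariates into the model without changing how they are measured: "For the SCRI and CCO, time-varying confounders will be adjusted for in regression models". The sensitivity analyses in Section 9.6.5 do not vary the covariate windows. Section 9.8 concedes time-varying confounding in general terms and ties it to sources that lack the data. Section 9.2.3.2 starts CCO follow-up at the beginning of the comparison window and asks for exposure data back to that point only.

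**The concern.** How long an infection or another vaccine raises the risk of the event does not depend on which design analyses the data. The CCO rule ties that period to how long the COVID-19 vaccine is thought to act, and no reason is given for departing from the SCRI rule. When the two periods differ, a confounder that is still acting at the event can be coded as absent, and the regression term cannot remove its effect.

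Table 2 (Section 9.1) makes the CCO the primary analysis in two scenarios. Where no trends are observed, there is no secondary analysis. Where trends cannot be checked but are not suspected, the SCRI is the secondary analysis. In a safety study the stakes run both ways: a real risk may be understated, or a signal may appear where there is none.

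**Working it through.** The protocol gives no figure on this point, so there is none to reproduce. The check has four steps.

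**1. What the rule leaves out.** Inputs from Section 9.2.5.3: exposure window 1-21 days and comparison window 50-70 days before the event. Assumed: the infection raises risk for days 1-42.

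- Infection days that matter at the event: 42. Days assessed: 21. Days 22-42 (42 − 22 + 1 = 21 days, half the risk period) fall in neither window.
- The comparison window is shifted by 50 − 1 = 49 days, so the matching infection period is days 50 to 49 + 42 = 91. The rule assesses 50-70 and omits 71-91.

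**2. What that does in the model.** With one comparison window, each case contributes

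1 / (1 + exp{−β(E1 − E0) − γ(C1 − C0)}),

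where E is COVID-19 vaccination and C the covariate, in the exposure (1) and comparison (0) windows. An infection on day 30 gives C1 = C0 = 0, so γ drops out. Suppose infection cuts vaccination to 10% of its usual rate for 28 days, counting the infection day (days 30 to 3). Then 19 of the 21 exposure-window days are affected and none of the comparison days. For that case, with no vaccine effect, the expected exposure-to-comparison ratio is (2 + 19 × 0.1)/21 = 3.9/21 = 0.19 instead of 1, and the model treats the case as uninfected.

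**3. Size under strong confounding.** All inputs other than the protocol's windows are assumptions. Vaccination has no calendar trend.

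*Infection defers vaccination, exact expected-likelihood calculation.* Windows 1-21 and 50-70, infection window 1-42, vaccination cut to 10% for 28 days:

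| Infection rate per day | Infection RR | Protocol rule, true RR 1.5 |
|---|---|---|
| 0.0005 | 5 | 1.46 |
| 0.0005 | 20 | 1.32 |
| 0.002 | 5 | 1.35 |
| 0.002 | 20 | 1.03 |

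Own-window coding returns 1.50-1.51. For a true RR of 2, the protocol rule gives 1.94 down to 1.37, and own-window coding 2.00-2.01.

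*Infection defers vaccination, Monte Carlo, true OR 1.* 20% infected over 200 days, 3,000,000 persons per scenario:

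| Scenario | Unadjusted | Protocol rule | Own window |
|---|---|---|---|
| 7-day windows 14 days apart, risk ×10 for 28 days | 0.85 | 0.85 | 0.99 |
| 7-day windows 28 days apart, same infection | 0.81 | 0.84 | 1.01 |
| Windows 35 days apart, 42-day effect and deferral | 0.74 | 0.76 | 1.02 |
| 21-day windows, 42-day effect | 0.88 | 0.95 | 1.00 |
| 7-day windows 14 days apart, risk ×5 | 0.92 | 0.92 | 1.00 |

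*Covariate window wholly outside the vaccine window* (15-42 against 1-7): the most extreme case gives 1.04 both unadjusted and adjusted for a true 1.5, so adjustment does nothing.

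*Other vaccine clustering with COVID-19 vaccination* (given the same day or within 28 days before, five-fold excess), windows 1-21 and 50-70: a true RR of 1 is estimated at 1.13-2.16, against 1.01-1.04 with own windows. The bias is now upward.

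**4. Where the problem shrinks.**

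- Windows coincide (both 1-42), infection deferring vaccination: 1.49-1.50 for a true 1.5.
- Covariate window shorter (1-7 against 1-42), same mechanism: 1.50-1.54 for a true 1.5.
- Risk ×3, 10% infected, half deferring for 14 days: 1.00-1.01 for a true 1.0, level with own-window coding.
- Windows 1-21 and 50-70, risk ×5, 5% infected, full 28-day deferral: 0.99 against 1.00.

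**The case against.** **The sentence may mean something else.** Status during the window could mean being within the infection's own risk period at that time, not having its onset there. In a simulation with risk ×10, 20% infected, full 28-day deferral and 7-day windows 14 days apart, that reading gave 0.96 for a true 1.0, against 0.89 when onset is coded. The reading is possible. However, the text attaches the confounder-specific window to the SCRI only and names the COVID-19 windows as the assessment period for the CCO. If the milder meaning was intended, the sentence still needs to say so.

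**This is a template.** Section 8 allows wording to be modified, and Section 9.2.5.5 asks investigators to supply operational definitions. That gives room for repair. But the CCO rule is written as settled text, and the bracketed note does not reopen it.

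**The inputs are strong.** This stands. The larger biases need heavy confounding, and step 4 shows how quickly they fade.

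**Stronger readings that the documents do not support.**

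- A reader might infer that the rule can make matters worse by correcting in the wrong direction. In all five Monte Carlo scenarios the adjusted estimate equals the unadjusted one or lies closer to 1. In the exact calculations, where the adjusted estimate is further from the truth than the unadjusted one, it is so by only about 0.02 (for example 1.48 to 1.54 for a true 1.5).
- A reader might infer that the error only hides risks. Clustered vaccines produce the opposite.
- A reader might infer that any disagreement between CCO and SCRI would then be purely a coding artefact. Table 2 pairs the two in only one of the two CCO-primary scenarios, and Section 9.2.5.5 expects some hospitals to be unable to adjust the SCRI for infections at all.

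**Conclusion.** The point holds in a conditional form. Section 9.2.5.5 fixes a CCO measurement rule that differs from its SCRI rule for the same confounders, and no other section repairs it. Harm needs two things together: a confounder whose risk period differs from the COVID-19 window, mainly by being longer or later, and an association between that confounder and the timing of COVID-19 vaccination.

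Under strong assumed confounding the error is large enough to change a conclusion in either direction. Under mild confounding it is negligible. The sizes illustrate the mechanism and do not predict the bias in any given study, since the protocol gives no infection rates, relative risks or deferral patterns. The documents do not support a claim that the CCO adjustment fails in general. The rule should be corrected before the template is adopted, because the problem remains even where the covariate data are complete.

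**What to change.** In Section 9.2.5.5, replace the CCO sentence with wording to this effect: *In the CCO, each infection and each non-COVID-19 vaccine is assessed over its own risk window (the same as in the SCRI), counted back from the event date for the exposure window, and from the matching reference date at the end of the comparison window for the comparison window.*

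In Section 9.2.3.2, extend the covariate look-back to the longest such window before the comparison reference date. With the example windows and an assumed 42-day infection window, the reference date is 49 days before the event, so covariate data are needed back to day 91 instead of day 70, which is 21 days more.

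The cost is two short text changes and a longer look-back. Some cases or sites may lack the earlier data, particularly as infection capture from primary care is already only where feasible.

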9.3 Data Sources

A feasibility questionnaire (Annex 5) will be distributed to candidate hospital sites before the initiation of the study to identify suitable sites for the study. Data sources will include hospital discharge databases and other electronic data sources that capture diagnoses and treatments in the inpatient, emergency department and speciality ambulatory care settings at the participating hospital site, medical records, vaccination cards, immunisation registers, and other secondary data sources. To participate in this study, data sources must have the ability to capture data on COVID-19 vaccinations (including the ability to distinguish between individual products and identify the date of vaccination) and adverse events of interest as treated in the hospital. The ability to conduct follow-up on exposures, outcomes, and time-varying covariates after discharge will be assessed in the feasibility assessment for informational purposes, though it will not be a prerequisite to participate in the study if the vaccinated case-coverage or CCO design is used, or if the assumptions for the SCRI (described in Annex 3) are met. Data sources must also have the ability to conduct case adjudication to confirm cases and to assign onset dates if available in medical charts.

The data sources for the exposures, outcomes, and covariates will be listed in this section, including coding systems, data lag, and starting date of data availability. The size of the database and number of COVID-19 vaccinations by age and comorbidities of interest in the most recent data update will be included in this section. Validation data on relevant data elements will also be described if available.

